#### 1.9.2 Laboratory data

The summary of laboratory evaluations will be presented for three groups of laboratory tests (hematology, clinical chemistry and urinalysis). The results will be provided separately for each study period by study visit and treatment group using the treatment groups defined in Section 1.9.

Descriptive summary statistics for the change from baseline to each study visit will be presented by laboratory test and treatment group for all non-categorical parameters. Change

from baseline will only be summarized for subjects with both baseline and post baseline values and will be calculated as:

change from baseline = post baseline value – baseline value

Clinically notable laboratory values will be analyzed for the following laboratory parameters with respect to the criteria given in Table 1-10: alanine aminotransferase (ALT), aminotransferase (AST), total bilirubin (TBL), alkaline phosphatase (ALP), creatinine (serum), potassium, sodium, hemoglobin (HGB), platelets, white blood cell count, neutrophils, eosinophils, lymphocytes and protein urine. The number and percentage of subjects with clinically notable laboratory value newly occurring or worsening after baseline will be presented. These summaries will be split into *liver function and related variables*, renal function and electrolyte variables, hematology variables and urinalysis variables.

Table 1-10 Criteria for notable laboratory parameters to be analyzed

Variable	Criterion for notable value
Liver function and related variables	
ALT increased	>3.0 x Upper Limit of Normal (ULN)
AST increased	>3.0 x ULN
Total bilirubin (TBL) increased	>2.0 x ULN
ALP increased	>2.5 x ULN
Renal function and electrolyte variables	
Creatinine increased	>1.5 x ULN
Potassium abnormal	> 6 mmol/L or <3 mmol/L
Sodium abnormal	>160 mmol/L or < 115 mmol/L
Hematology variables	
HGB decreased	≥20 g/L decrease from Baseline
Platelet count decreased	< Lower Limit of Normal (LLN)
White blood cell decreased	<0.8 x LLN
Neutrophil decreased	<0.9 x LLN
Eosinophils increased	>1.1 x ULN
Lymphocytes increased	>1.1 x ULN
Urinalysis variable	
Protein urine dipstick	≥ 100 mg/dL (++)

The number and percentage of subjects with notable laboratory value newly occurring or worsening after baseline will be presented.

Newly occurring liver enzyme abnormalities will also be summarized based on the event criteria given in Table 1-11. For a combined criterion to be fulfilled, all conditions have to be fulfilled on the same visit. The criteria are not mutually exclusive, e.g., a subject with ALT = 6.42xULN is counted for ALT >3xULN and ALT>5x ULN.

Individual subject data listings will be provided for subjects with abnormal laboratory data. Data of subjects with newly occurring liver enzyme abnormalities will be provided in an additional listing.

Table 1-11 Liver-related events

Parameter	Criterion
ALT or AST	>3xULN; >5xULN
TBL	>1.5xULN; >3xULN,
ALP	>2xULN; >5xULN
ALT or AST & TBL & ALP	ALT or AST>3xULN & TBL >2xULN & ALP ≤2xULN (Hy's Law)

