#### 1.4.3 Screening, baseline and post-baseline definitions

Screening refers to any procedures (e.g., checking inclusion and exclusion criteria) performed prior to the date of visit 2. Per protocol, subject informed consent must be obtained prior to performing any study related activity. The date of signing informed consent is the start date of screening period. Any assessment obtained during the screening period will be labeled screening assessment.

Visit 2 is defined as *Baseline* visit. All consecutive visits are labeled according to the preplanned study week where they occur, i.e. Week 1, Week 2, and so on.

Week 24 is defined as the end of Treatment Period 1 (visit 11) for patients without premature discontinuation during Treatment Period 1. For patients with premature termination within Treatment Period 1 the last visit is defined as end of Treatment Period 1.

Week 52 is defined as the end of Treatment Period 2 (visit 18) for patients without premature discontinuation during Treatment Period 2. For patients with premature termination in Treatment Period 2 the last visit is defined as end of Treatment Period 2.

Any visits and assessments occurring after the end of Treatment Period 2 visit (Week 52 in the eCRF) will be aligned to the Week 60 Follow-Up visit.

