#### 1.4.4 Analysis Visits windows

*Visit-windows* will be used for the data that is summarized by visit; they are based on the study evaluation schedule and comprise a set of days around the nominal visit day. The visit windows for Treatment Period 1 and Treatment Period 2 are shown in Table 1-3. In this table, the days are counted since the first dose of study treatment (study days).

When visit windows are used, all visits will be re-aligned, i.e., they will be mapped into one of the visit windows. E.g., if the *Week 4* visit of a subject is delayed and occurs on Day 46 instead of on Day 29, say, it will be re-aligned to visit window *Week 8*. In the case of major deviations from the visit schedule, or due to unscheduled visits, several assessments of a subject may fall in a particular visit window (either scheduled or unscheduled). Statistical approaches to handle multiple assessments in a given visit window are specified in Section 1.4.5.

Table 1-3 Analysis windows for scheduled visits

Analysis Visit	Week	Scheduled Day	Analysis Window
Screening	-4 to BSL		-28 days to Day 1
Baseline*	BSL	1	
Week 1	1	8	Day 2-11
Week 2	2	15	Day 12-18
Week 3	3	22	Day 19-25
Week 4	4	29	Day 26-43
Week 8	8	57	Day 44-71
Week 12	12	85	Day 72-99
Week 16	16	113	Day 100-127
Week 20	20	141	Day 128-155
Week 24	24	169	Day 156-183**
Week 28	28	197	Day 184-211
Week 32	32	225	Day 212-239
Week 36	36	253	Day 240-267
Week 40	40	281	Day 268-295
Week 44	44	309	Day 296-323
Week 48	48	337	Day 324-351
Week 52	52	365	Day 352-379

\* Baseline measurement before the first drug administration. The days are counted since the first dose of study treatment.

For parameters which are not collected at every visit (e.g. DLQI, WPAI-PSO), visit windows defined in Table 1-3 will be combined. For example, if a parameter is measured at Week 24, Week 36 and Week 48, but not in between (i.e. Week 28, Week 32, Week 40 and Week 44), the Week 36 visit window will extend from Day 212 to Day 295 (combining Week 32 to Week 40 visit windows). If more than one assessment falls into the interval, the rules defined in Section 1.4.5 below are applied.

Assessments from Treatment Period 2 will not be considered for Treatment Period 1 and Treatment Period 1 visits will not be mapped into Treatment Period 2. For example, if a Week 28 (scheduled visit) measurement falls into the Week 20 visit window, this measurement would not be analyzed as Treatment Period 1 value.

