#### 1.9 Standard safety evaluation

Safety analyses will be performed separately for Treatment Period 1, Treatment Period 2 and the Follow-Up period. Additionally, adverse events will be analyzed for the Entire Study Period combined (i.e. Treatment Period 1, Treatment Period 2).

Safety analyses for Treatment Period 1 will be based on the SAF-TP1, for Treatment Period 2 on the SAF-TP2, analyses for the post treatment Follow-Up period on the FUS and analyses for the Entire Treatment Period on the SAF-TP1.

#### Treatment groups for evaluation of Treatment Period 2

For safety-evaluations, the patient groups of PASI 90 responders and those who achieve PASI 75 but not PASI 90 will be pooled for Group 1 and Group 3; therefore, only 3 dosing groups will be analyzed in Treatment Period 2:

- Secukinumab 300 mg s.c. every 2 weeks (patients from Group 4).
- Secukinumab 300 mg s.c. every 4 weeks (patients from Group 1 pooled with Group 3).
- Secukinumab 300 mg s.c. every 6 weeks (patients from Group 2).

Additionally, the total number of patients over all groups will be analyzed in a separate column. Patients will be analyzed according to the treatment regimen they received.

If the treatment regimen of patients only deviates partially from the randomized treatment regimen during Treatment Period 2, these patients will be analyzed according to the treatment randomized.

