#### 1.9.1 Adverse events

For adverse events and other binary safety variables crude incidence rates and associated 95%-CIs will be derived.

The crude incidence of treatment emergent adverse events will be summarized by primary System Organ Class (SOC) and Preferred Term (PT). Only primary paths within MedDRA will be considered for AE reporting.

Treatment emergent adverse events are AEs which started after the first dose of study medication or events present prior to the first dose of study medication but increased in severity based on preferred term during the Treatment Period 1, Treatment Period 2 or Follow-Up Period.

The assignment of an AE to a specific treatment period is according to its start date: an AE with start date in Treatment Period 1 and ongoing in Treatment Period 2 will count for Treatment Period 1. Only in case of increased severity in Treatment Period 2 it will also count for Treatment Period 2.

AEs will be summarized by presenting, for each treatment group (including "any AIN457"), the number and percentage of subjects having at least one AE, having an AE in each primary SOC and having each individual AE (preferred term). Summaries will also be presented for AEs by severity and for study treatment related AEs, i.e. AEs for which a possible causal relationship to the study drug has been stated in the eCRF. If a particular AE 'severity' is missing, this variable will be listed as missing and treated as missing in summaries.

If a subject reported more than one adverse event with the same preferred term, the adverse event with the greatest severity will be presented. If a subject reported more than one adverse event within the same primary system organ class, the subject will be counted only once with the greatest severity at the system organ class level, where applicable. The same algorithm applies to study treatment related AEs.

The MedDRA version used for reporting the adverse events will be described in a footnote.

Separate summaries will be provided for deaths, serious adverse events and adverse events leading to study drug discontinuation.

The adverse events will be summarized as crude incidence rates by subgroup as indicated in Table 1-1.

Non-treatment emergent adverse events will be summarized as well. These adverse events occurring before the first dose of the study treatment will be listed.

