#### 1.9.3 Vital signs

Analysis in vital sign measurement using descriptive summary statistics for the change from baseline for each post-baseline visit will be performed by vital sign. Change from baseline will only be summarized for subjects with both baseline and post-baseline values and will be calculated as:

change from baseline = post-baseline value – baseline value

The Body Mass Index (BMI) will be calculated using the following formula:

BMI  $(kg/m^2) = (body weight in kilograms) / (height in meters)^2$ 

The number and percentage of subjects with newly occurring notable vital signs will be presented. Criteria for notable vital sign abnormalities are provided in Table 1-12 below.

Table 1-12 Criteria for notable vital sign abnormalities

Description of abnormality	Notable abnormalities
Hypertension	Systolic blood pressure ≥ 140 mmHg or diastolic blood pressure ≥ 90 mmHg
Hypotension	Systolic blood pressure < 90 mmHg or diastolic blood pressure < 60 mmHg
Abnormal pulse	> 100 bpm or <60 bpm

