### 1.9.4 Electrocardiogram (ECG)

The following quantitative variables will be summarized: RR interval, PR interval, QRS duration, QT interval (QT), corrected QT interval using Fredericia's formula (QTcF) and heart rate (HR).

QTcF will be summarized by computing the number and percentage of subjects with:

- QTcF > 500 msec
- QTcF > 480 msec
- OTcF > 450 msec
- QTcF changes from baseline > 30 msec
- OTcF changes from baseline > 60 msec
- ◆ PR > 250 msec

Summary statistics will be presented for ECG variables by visit and treatment group.

In addition, shift tables comparing baseline ECG results (normal, abnormal, not available, total) with the result at Week 24 and at Week 52 (normal, abnormal, not available, total) will be provided.

A listing of all newly occurring or worsening abnormalities will be provided.

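### Treatment Period 2 safety tables judge new or worse notable laboratory values against Day 1, so persistent run-in abnormalities are counted under the randomised regimens

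*SAP*

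**What the plan says.** SAP 1.4.3 sets a single reference point: "Visit 2 is defined as *Baseline* visit". The footnote to SAP Table 1-3 fixes its timing: "Baseline measurement before the first drug administration. The days are counted since the first dose of study treatment". Week 24 is defined only as the end of Treatment Period 1; no second baseline is set for the randomised period.

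SAP 1.9 splits the reporting: "Safety analyses will be performed separately for Treatment Period 1, Treatment Period 2 and the Follow-Up period". Treatment Period 2 is shown in three columns: 2-weekly (Group 4), 4-weekly (Groups 1 and 3 pooled) and 6-weekly (Group 2).

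The counting rules within those tables are:

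- Laboratory (SAP 1.9.2): "The results will be provided separately for each study period by study visit and treatment group". The rule for notable values is: "The number and percentage of subjects with clinically notable laboratory value newly occurring or worsening after baseline will be presented". The haemoglobin criterion in Table 1-10 is itself a fall from Baseline.
- Vital signs (SAP 1.9.3): "The number and percentage of subjects with newly occurring notable vital signs will be presented". No reference is named.
- ECG (SAP 1.9.4): counts use absolute thresholds and change, for example "QTcF changes from baseline > 30 msec".
- Adverse events (SAP 1.9.1): "an AE with start date in Treatment Period 1 and ongoing in Treatment Period 2 will count for Treatment Period 1". Such an event is counted again in Treatment Period 2 only if its severity increases there.

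**The concern.** Up to Week 24 every patient is on the same regimen. An abnormality that arises then cannot be an effect of the regimen assigned at Week 24. The SAP applies that reasoning to adverse events but has no equivalent rule for laboratory, vital-sign or ECG findings.

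What is at stake is how readable the regimen comparison is. Protocol 2.3 lists the safety and tolerability of the maintenance regimens as an objective. Protocol 3.3 notes that the 2-weekly regimen has not yet been tested in maintenance. Protocol 3.6 reports slightly more mild to moderate neutropenia than on placebo, and neutrophils are among the notable parameters. A shared background carried in from the run-in makes every column look worse and the columns look more alike.

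**Working it through.** **Tracing one patient.** Protocol Table 6-1 schedules safety laboratory samples at Baseline and Weeks 4, 12, 16, 24, 28, 36, 48 and 52. Take a patient with a normal value on Day 1, a notable value at Weeks 12 and 24, and the value still notable at Week 28.

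| Finding | Rule | Counted in Treatment Period 2? |
|---|---|---|
| Notable laboratory value | new or worse since Day 1 | Yes, under the assigned regimen |
| Adverse event, same dates | assigned by start date | No, unless severity rises |

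A value that has returned to normal by Week 24 and stays normal is not carried over. The effect is confined to abnormalities that persist or recur.

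**ECG.** ECGs are scheduled only at Baseline and Weeks 24, 52 and 60. A QTcF increase above 30 msec present at Week 24 and again at Week 52 is counted in Treatment Period 2, because both changes are taken from Day 1.

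**Size.** The plan gives no figure to reproduce and no rates. All rates below are assumptions. Let c be the share of patients whose notable value arose before Week 24 and is still present afterwards, and r the risk of a truly new finding among the others. The rate shown is c + (1 − c) × r. For c = 2% and r = 2% v 4%: 0.02 + 0.98 × 0.02 = 3.96%, and 0.02 + 0.98 × 0.04 = 5.92%, a ratio of 1.49.

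| c | True 2% v 4%: shown | Ratio | Difference (points) | True 5% v 10%: shown | Ratio | Difference (points) |
|---|---|---|---|---|---|---|
| 0 | 2.00% v 4.00% | 2.00 | 2.00 | 5.00% v 10.00% | 2.00 | 5.00 |
| 1% | 2.98% v 4.96% | 1.66 | 1.98 | 5.95% v 10.90% | 1.83 | 4.95 |
| 2% | 3.96% v 5.92% | 1.49 | 1.96 | 6.90% v 11.80% | 1.71 | 4.90 |
| 5% | 6.90% v 8.80% | 1.28 | 1.90 | 9.75% v 14.50% | 1.49 | 4.75 |
| 10% | 11.80% v 13.60% | 1.15 | 1.80 | 14.50% v 19.00% | 1.31 | 4.50 |

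With equal c, the ratio is diluted but the difference is multiplied only by (1 − c).

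**Patients involved.** Planned sizes are 570 in each of Groups 1 and 2 (SAP 1.11) and 105 in each of Groups 3 and 4 (Protocol 9.7.1). The columns then hold 570 (6-weekly), 570 + 105 = 675 (4-weekly) and 105 (2-weekly). At c = 2% the carried-over patients number 11.4, 13.5 and 2.1.

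**Unequal carry-over.** Randomisation balances c within Groups 1 and 2 and within Groups 3 and 4, but not across the three safety columns. Assume c = 2% in PASI 90 responders and 5% in partial responders. The columns carry 2.0% (6-weekly), (570 × 0.02 + 105 × 0.05)/675 = 2.5% (4-weekly) and 5.0% (2-weekly). If truly new findings were 2% everywhere, the 2-weekly column would show 0.05 + 0.95 × 0.02 = 6.9%, and the 4-weekly column 0.0247 + 0.9753 × 0.02 = 4.4%, with no regimen effect at all. If carry-over were higher in responders, the distortion would run the other way.

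**The case against.** A drug-free baseline is a defensible convention, and several features of the plan limit the damage. Laboratory data are also summarised by visit and group, with listings of abnormal values. Clinically significant abnormalities are adverse events (Protocol 7.1) and so follow the start-date rule. SAP 1.9.4 plans ECG shift tables to Week 24 and to Week 52. Protocol 3.6 describes most grade 3 neutropenia as transient and reversible, and Protocol 5.5.10 and Appendix 2 stop study drug for some abnormalities, so some affected patients never reach randomisation. SAP 1.9.1 plans crude incidences with confidence intervals, not risk ratios, and differences are barely attenuated when carry-over is equal. Finally, pooling Groups 1 and 3 already makes the columns non-randomised comparisons, and a new reference value does not cure that. All of this stands, and it is why the point is minor. None of it removes the mismatch with the adverse event rule.

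Three stronger readings are tempting but not supported:

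- A reader might infer that QTcF findings first seen at Weeks 4 to 20 are counted as new at Week 28. No ECG is scheduled at those visits, and in SAP 1.9.4 the new-or-worse wording governs only a listing, not the counts.
- A reader might infer that the SAP states a Day 1 reference for vital signs. SAP 1.9.3 is silent; Day 1 follows only from the single baseline definition.
- A reader might infer that the Day 1 reference can simply be replaced, because combined-period tables would still show change from the untreated state. SAP 1.9 plans the combined analysis for adverse events only, and without regimen groups. Replacement would also lose cumulative change: a haemoglobin fall of 12 g/L before Week 24 and 10 g/L after totals 22 g/L and meets the 20 g/L criterion from Day 1, but not from Week 24.

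**Conclusion.** The point holds, as a minor one. For laboratory values it follows directly from the text. For QTcF change it holds at Week 52 when the prolongation was already present at Week 24. For vital signs it holds if the single baseline definition is applied, and is otherwise an ambiguity to settle.

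The effect is to inflate each Treatment Period 2 column and dilute relative contrasts between regimens, possibly unequally because the columns mix responder groups. Its size cannot be known from the documents. In the assumed range of 1% to 10% carry-over, a true ratio of 2.00 shows as 1.15 to 1.83, with risk differences reduced by 1% to 10% of their value. A reader might infer that a safety difference would be hidden, or that the trial's conclusions are at risk. The documents do not support either: they give no incidence or persistence rates, and these tables are descriptive and stand outside the primary and key secondary tests.

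**What to change.** In SAP 1.4.3, define a Treatment Period 2 reference as the last value before the Week 24 dose. Use it in the Treatment Period 2 tables to count new or worse notable laboratory values (SAP 1.9.2) and vital signs (SAP 1.9.3) and QTcF change (SAP 1.9.4), in line with the adverse event rule. State the reference explicitly in SAP 1.9.3.

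Keep the Day 1 change-from-baseline summaries and the protocol's haemoglobin criterion, by regimen, alongside these counts.

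No new data are needed. Protocol Table 6-1 schedules laboratory samples, vital signs and ECG at Week 24; Protocol 6.5 places safety assessments before dosing; and SAP Table 1-3 already excludes data after the date of the Week 24 dose from Week 24. The cost is one derived reference variable and a second set of counts, which need clear labels so that the two references are not confused.

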#### 1.9.3 Vital signs

Analysis in vital sign measurement using descriptive summary statistics for the change from baseline for each post-baseline visit will be performed by vital sign. Change from baseline will only be summarized for subjects with both baseline and post-baseline values and will be calculated as:

change from baseline = post-baseline value – baseline value

The Body Mass Index (BMI) will be calculated using the following formula:

BMI  $(kg/m^2) = (body weight in kilograms) / (height in meters)^2$ 

The number and percentage of subjects with newly occurring notable vital signs will be presented. Criteria for notable vital sign abnormalities are provided in Table 1-12 below.

Table 1-12 Criteria for notable vital sign abnormalities

Description of abnormality	Notable abnormalities
Hypertension	Systolic blood pressure ≥ 140 mmHg or diastolic blood pressure ≥ 90 mmHg
Hypotension	Systolic blood pressure < 90 mmHg or diastolic blood pressure < 60 mmHg
Abnormal pulse	> 100 bpm or <60 bpm

### 1.9.4 Electrocardiogram (ECG)

The following quantitative variables will be summarized: RR interval, PR interval, QRS duration, QT interval (QT), corrected QT interval using Fredericia's formula (QTcF) and heart rate (HR).

QTcF will be summarized by computing the number and percentage of subjects with:

- QTcF > 500 msec
- QTcF > 480 msec
- OTcF > 450 msec
- QTcF changes from baseline > 30 msec
- OTcF changes from baseline > 60 msec
- ◆ PR > 250 msec

Summary statistics will be presented for ECG variables by visit and treatment group.

In addition, shift tables comparing baseline ECG results (normal, abnormal, not available, total) with the result at Week 24 and at Week 52 (normal, abnormal, not available, total) will be provided.

A listing of all newly occurring or worsening abnormalities will be provided.

### 1.10 Compound specific safety evaluation

Safety topics of interest, such as risks defined in the Safety Profiling Plan, Risk Management Plan or topics of interest regarding signal detection or routine analysis are defined in the Program Case Retrieval Sheet that is stored in CREDI.

AEs of special interest (AESI) will be analyzed separately for Treatment Period 2 and the Entire Treatment Period. Crude incidence rates and corresponding confidence intervals of AESI will be summarized overall and by PT.

In addition, listings will be provided presenting which subjects experienced which risk.

The following AESI are part of the analysis.

- Major adverse cardiovascular events (MACE): identified per Novartis MedDRA Query (NMQ) "MACE (MI, Stroke, Cardiovascular death)"
- Inflammatory bowel disease: identified per NMQ "Inflammatory bowel disease"
- Candida infections: any AE with Candida high level term
- Malignancy: identified per NMQ "Malignant or unspecified tumours (excl. BCC and SCC)"
- Hypersensitivity and injection site reaction: identified per SMQ "Hypersensitivity"
- Hepatotoxicity: identified per SMQ "Drug related hepatic disorder severe events only"

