5.5.4 Instructions for prescribing and taking study drug

Secukinumab will be self-administered by patients during the study after the study assessments (including completion of PROs) and scheduled blood samples have been performed.

For Treatment Period 1, all patients will be assigned to the same study drug regimen (300 mg secukinumab s.c. every week for the first 4 weeks, and thereafter every 4 weeks) and will self-administer the study drug at the study site under the supervision and guidance of site personnel at the time-points indicated in Table 5-1. To allow for comparable treatment group data on fixed study visits, patients will be trained for home drug administration prior to Treatment Period 2. If needed, a caregiver can be trained for home administration to provide support to the patient; corresponding training should be documented in the source data at the study center.

For Treatment Period 2, patients will be assigned to 4 different treatment interval groups depending on their PASI response at Week 24. Patients will self-administer their first dose of randomized study drug at Week 24 at the study site under the supervision and guidance of site personnel. Thereafter, patients will self-administer the study drug at either the study site or at home depending on the scheduled study drug administration by study group in Table 5-1 and Table 6-2.

Table 5-1 Timing of study drug administration by study group

_		
	Treatment Period 1	
	(Self-administration at Study Site)	(Self-administration at Home)
All Patients		
All patients	Baseline and	None
	Weeks 1, 2, 3, 4, 8, 12, 16 and 20	
	Treatment	Period 2
	(Self-administration at Study Site)	(Self-administration at Home)
Patients with PASI ≥ 90		
Group 1 (every 4 weeks)	Week 24, 28, 32, 36, 40, 44 and 48	None
Group 2 (every 6 weeks)	Week 24, 36, 48	Week 30, 42
Patients with 75 ≤ PASI < 90		
Group 3 (every 4 weeks)	Week 24, 28, 32, 36, 40, 44 and 48	None
Group 4 (every 2 weeks)	Week 24, 28, 32, 36, 40, 44 and 48	Week 26, 30, 34, 38, 42 and 46

Study drug will be dispensed and self-administered with the support of qualified personnel during office visits in accordance with local laws and regulations or self-administered at home. The blinded assessor for PASI and IGA mod 2011 must not be part of the study drug dispensing or administration process.

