Vital signs	Χ	Х				Χ		Χ	Χ		Х	Χ		Χ			Χ	Х	Х	X	
Laboratory sampling: safety panel (Clinical chemistry including urine, hematology)	X	х				×		x	х		х	х		х			х	х	х	х	For processing of samples please refer to the manual of the central lab.

Period	Scr				Tre	atmen	t Perio	d 1						Treati	ment P	eriod 2	2		FU	it ^d	Comments
Visit	1	2	3	4	5	6	7	8	9	10	11	12	13	14	15	16	17	18	19	d Vis	
Week	-4 to BL °	BL	1	2	3	4	8	12	16	20	24 a, b	28	32	36	40	44	48	52 c	60	Unscheduled Visit ^d	
Recommended visit window (days)			±2	±2	±2	±2	±5	±5	±5	±5	±2	±5	±5	±5	±5	±5	±5	±5	±5	Nus	
Chest X-ray (or CT/MRI)	S																			S	Where a patient has not had a chest X-ray, chest CT or chest MRI, CT performed within 3 months prior to Screening, an image should be obtained once it is clear that the patient meets the other inclusion/exclusion criteria in order to minimize unnecessary exposure X-ray radiation.
QuantiFERON® TB-Gold In-tube test ^e	Х																			Х	see lab manual
Serum pregnancy test	Х																			Х	Only for females of child- bearing potential.
Urine pregnancy test (local)		x				x		x	x		х			x				x	x	х	In the event of a positive urine pregnancy test, study drug must be withheld and a serum pregnancy test performed at the same visit. A urine pregnancy test is not required for a woman who is sterile or who is postmenopausal.
ECG (standard 12-lead)		Х									Х							Х	Х	Х	
PASI	Х	Х	Х	Х	Х	Х	Х	Х	Х	Х	Х	Х	Х	Х	Х	Х	Х	Х	Χ	Х	
BSA	Х	Х																Х		Х	

Period	Scr				Tre	atmen	t Perio	d 1				Treatment Period 2								ita	Comments
Visit	1	2	3	4	5	6	7	8	9	10	11	12	13	14	15	16	17	18	19	d Vis	
Week	-4 to BL ^e	BL	1	2	3	4	8	12	16	20	24 a, b	28	32	36	40	44	48	52 c	60	Unscheduled Visit ^d	
Recommended visit window (days)			±2	±2	±2	±2	±5	±5	±5	±5	±2	±5	±5	±5	±5	±5	±5	±5	±5	Uns	
IGA mod 2011	Χ	Χ	Χ	Χ	Χ	Х	Χ	Х	Χ	Χ	Χ	Χ	Χ	Χ	Χ	Х	Χ	Х	Χ	Х	
DLQI		Х				Χ		Χ			Χ			Х			Χ	Х		Х	
WPAI-PSO		Х				Х		Χ			Χ			Χ			Χ	Χ		Х	
Assessment of pain, itching and scaling		Х				Х		Х			Х			Х			Х	Х		Х	
EQ-5D [©]		Х				Х		Х			Х			Х			Χ	Х		Х	
AE assessment (including injection site reactions)	х	х	х	х	х	Х	х	Х	Х	х	Х	х	х	х	х	Х	Х	Х	х	х	
Assessment of rebound																			x		Unscheduled rebound assessment only to be done at an unscheduled visit that occurs during the post-treatment follow-up period.
Randomization by IRT											Х										
IRT contact such as for registration or drug supply including home administration	х	х	х	х	х	x	х	x	х	x	х	х	x	х	x	x	x	х			

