### 1.2 Subjects and treatments

The following study periods will be considered for the analysis:

- Screening Period (Screening to Visit 2 [=Baseline], excluding Visit 2 [=Baseline])
- **Treatment Period 1** (Visit 2 [=Baseline] to Week 24 pre-dose)
- Treatment Period 2 (Week 24 post-dose to Week 52)
- Follow-Up Period (Week 52 to Week 60, excluding Week 52).

For Treatment Period 1 (Baseline to Week 24) all patients will receive the same treatment:

• Secukinumab 300 mg s.c. will be self-administered at Baseline, weekly at Week 1, Week 2 and Week 3 and every 4 weeks thereafter (i.e., Week 4, 8, 12, 16 and 20).

At Week 24, all patients will be assessed in term of PASI response and either randomized to one of the 4 treatment groups in Treatment Period 2 (Week 24 to Week 52) or withdrawn from the study. Randomization is stratified by body weight at this visit ("body weight  $\geq 90 \text{ kg}$ " vs. "body weight < 90 kg" at Week 24) in order to ensure balanced allocation of patients to treatment groups within the weight strata.

Patients with at least a 90% reduction in PASI score from Baseline will be randomized at Week 24 on a 1:1 basis to Group 1 or Group 2:

- **Group 1** (recommended maintenance treatment): secukinumab 300 mg s.c. every 4 weeks (Week 24, 28, 32, 36, 40, 44 and 48).
- **Group 2** (experimental dosing maintenance treatment): secukinumab 300 mg s.c. every 6 weeks (Week 24, 30, 36, 42 and 48).

Patients with less than 90% reduction in PASI score from Baseline at Week 24 but who achieved at least a 75% reduction in PASI score from Baseline are eligible for dose frequency intensification and will be randomized on a 1:1 basis to either Group 3 or Group 4:

- **Group 3** (recommended maintenance treatment): secukinumab s.c. 300 mg every 4 weeks (Week 24, 28, 32, 36, 40, 44 and 48).
- **Group 4** (experimental maintenance treatment): secukinumab s.c. 300 mg every 2 weeks (Week 24, 26, 28, 30, 32, 34, 36, 38, 40, 42, 44, 46 and 48).

Patients with a reduction in PASI score from Baseline of less than 75% at Week 24 are not eligible for randomization and are discontinued from the study.

The following analysis sets will be used for the data analysis.

Safety set for Treatment Period 1 (SAF-TP1): The safety set for Treatment Period 1 includes all subjects who took at least one dose of study treatment during this treatment period.

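### The special-interest topic in SAP 1.10 names injection site reactions but is searched only with a hypersensitivity query, and the SAP plans no count of patients with an injection site reaction by dosing group

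*SAP*

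**What the plan says.** SAP 1.10 lists six topics of special interest, each with a search strategy. One reads "Hypersensitivity and injection site reaction: identified per SMQ 'Hypersensitivity". No second query, high level term or list of preferred terms is given for the injection-site half. By contrast, the Candida topic in the same list is defined by a high level term.

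On reporting, the section says "Crude incidence rates and corresponding confidence intervals of AESI will be summarized overall and by PT", for Treatment Period 2 and for the entire treatment period. It also says that safety topics of interest "are defined in the Program Case Retrieval Sheet that is stored in CREDI". That sheet is not part of the SAP.

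On collection, the assessment schedule in Protocol Table 6-1 has a row for "AE assessment (including injection site reactions"), marked at every scheduled visit. Protocol 6.5 uses narrower wording and speaks of hypersensitivity reactions at the injection site.

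SAP 1.9 compares three regimens in Treatment Period 2: every 2 weeks (Group 4), every 4 weeks (Groups 1 and 3 pooled) and every 6 weeks (Group 2). SAP 1.9.1 tabulates all treatment-emergent adverse events by primary system organ class and preferred term in these groups, with crude incidence and 95% confidence intervals.

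**The concern.** The label of the topic is wider than its search. A reader of the results would take the line to cover injection site reactions in general, as collected under Table 6-1. The search, judged by its name, is aimed at allergic events. Pain, bruising or swelling at the site without an allergic mechanism may not be retrieved.

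This matters more here than in most trials. Within each randomised pair the arms receive the same drug at the same 300 mg dose and differ only in how often it is injected. Safety and tolerability of the different maintenance regimens is a stated exploratory objective (Protocol 2.3, SAP 1.1). A count of patients with a local reaction, by regimen, is a natural tolerability figure for that question. The only planned line that bears the name may not deliver it.

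**Working it through.** **Label against search.** The documents use two phrases. Table 6-1 refers to injection site reactions without qualification. Protocol 6.5 qualifies them as hypersensitivity reactions. The SAP topic takes the unqualified phrase for its label and a query suited to the qualified one. The SAP's document history records the specification of search strategies for these topics as a change in version 2.0, so what stands in SAP 1.10 is a stated rule rather than a placeholder.

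**What the general tables supply.** SAP 1.9.1 gives patient counts at three levels: any event, each primary system organ class, each preferred term. An injection-site total lies between the last two. It cannot be recovered exactly from the preferred-term rows, because a patient with two different site terms appears in two rows. From those rows alone, the number of patients with at least one site reaction lies between the largest single row and the sum of the rows.

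**Exposure to injections.** The plan states no ratio, so there is no figure to reproduce. The inputs are the Treatment Period 2 schedules in SAP 1.2 and the two syringes per 300 mg dose in Protocol 5.1.1.

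- Group 4: "300 mg every 2 weeks (Week 24, 26, 28, 30, 32, 34, 36, 38, 40, 42, 44, 46 and 48"), which is 13 doses; 13 × 2 = 26 syringes.
- Groups 1 and 3: for Group 1 "secukinumab 300 mg s.c. every 4 weeks (Week 24, 28, 32, 36, 40, 44 and 48"), and Group 3 has the same weeks, which is 7 doses; 7 × 2 = 14 syringes.
- Group 2: "secukinumab 300 mg s.c. every 6 weeks (Week 24, 30, 36, 42 and 48"), which is 5 doses; 5 × 2 = 10 syringes.

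Protocol 5.5.4 says that after the first randomised dose "Thereafter, patients will self-administer the study drug at either the study site or at home". Adding the site and home columns of its Table 5-1 gives the same totals: 7 + 6 = 13, 7 + 0 = 7 and 3 + 2 = 5.

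| Comparison | Ratio of scheduled doses | Randomised? |
|---|---|---|
| Group 4 vs Group 3 | 13/7 = 1.86 | Yes |
| Group 1 vs Group 2 | 7/5 = 1.40 | Yes |
| Group 4 vs Group 2 | 13/5 = 2.60 | No |

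Groups 4 and 2 come from different Week 24 response strata and are never randomised against each other. The counts assume that every scheduled dose is given.

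**The case against.** The strongest reply is that the query's content is unknown. The term list is not in the documents and neither is the Program Case Retrieval Sheet; either might include injection-site terms. This stands, and it limits the point to a possible gap of unknown size.

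A second reply is that Protocol 6.5 may show what was meant: allergic reactions at the site, for which the query fits and the SAP label is loose shorthand. That is possible. The documents do not settle it, since Table 6-1 uses the wider phrase. On this reading the label still needs correcting.

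A third reply is that nothing is lost, because every preferred term is tabulated by dosing group under SAP 1.9.1, and also by severity and by relation to study treatment. This is right about individual events. It does not supply a patient-level total.

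Two stronger readings are tempting. A reader might infer that the topic will count no non-allergic local reactions and so understate harm, most of all in the 2-weekly regimen, and might attach percentages by assuming a risk per injection. The documents give no such risk and do not show what the query leaves out, so neither the claim nor any percentage is supported. A reader might also quote the 2.6-fold ratio as the trial's contrast in injection exposure. It is exact arithmetic, but it compares groups that were not randomised against each other.

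**Conclusion.** The point holds as a mismatch between a topic and its stated search. The labelled line may be incomplete for injection site reactions by an amount that cannot be computed, and the SAP plans no count of patients with at least one such reaction by dosing group. That non-allergic local reactions fall outside the query is an assumption drawn from the query's name. The absence of a planned patient-level count, as a defined line of its own, does not depend on that assumption.

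The consequence is small. It affects one summary line and leaves the primary and key secondary analyses untouched, and the underlying events remain visible by preferred term. It is worth correcting because scheduled injections differ 1.86-fold and 1.40-fold within the randomised pairs, and tolerability of the regimens is a stated objective.

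**What to change.** Split the topic in SAP 1.10 into two:

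- Hypersensitivity, retrieved by the existing standardised query.
- Injection site reactions, retrieved by a MedDRA high level term, as is already done for Candida, or by a preferred-term list written into the SAP.

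For each, report the number and percentage of patients with at least one event by dosing group, using the crude incidence and confidence interval already planned. If the sponsor meant only allergic events, the minimum change is to rename the topic to match its query.

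The cost is a line of SAP text and one extra table row, with no new data. Some events may be counted under both topics; a footnote stating that the two overlap would deal with this.
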